IRB Minimal Risk Protocol Template

Note: If this study establishes a human specimen repository (biobank) for research purposes, do not use this template. Use the Mayo Clinic Human Specimen Repository Protocol Template found on the IRB home page under Forms and Procedures at <http://intranet.mayo.edu/charlie/irb/>

First-time Use: Use this template to describe your study for a new IRB submission.

1. Complete the questions that apply to your study.
2. Save an electronic copy of this protocol for future revisions.
3. When completing your IRBe application, you will be asked to upload this document to the protocol section.

Modification: To modify this document after your study has been approved:

1. Open your study in IRBe. Click on the study 'Documents' tab and select the most recent version of the protocol. Save it to your files.
2. Open the saved document and activate "Track Changes".
3. Revise the protocol template to reflect the modification points, save the template to your files
4. Create an IRBe Modification for the study and upload the revised protocol template.

General Study Information

Principal Investigator: [name]

Study Title: Clinical Validation Study for Noninvasive Cardiopulmonary Management Device (Phase II)

Sponsor: Analog Devices, Inc.

Clinical Research Organization: N/A

Protocol version number and date: 1.0 – February 7, 2022

Research Question and Aims

Hypothesis:

It is hypothesized that the ADI CPM System (test device) will be able to measure in healthy human volunteers:

- a) Respiration Rate (RR) with sufficient accuracy
- b) Changes in relative Tidal Volume (rTV) with sufficient accuracy

Objectives:

Primary Objectives

- 1) Validate Respiration Rate (RR) accuracy derived by the Cardiopulmonary Management (CPM) System in the range of 6-40 BPM
- 2) Validate relative changes in relative Tidal Volume (rTV) derived by the CPM System

*Secondary Objectives**

- 1) Confirm the ECG capabilities of the CPM System
- 2) Confirm the Skin temperature capability of the CPM system

Outcome Measures:

Primary Outcome Measures

- 1) Accuracy of CPM System calculated RR versus reference device
 - Proportion of the error within ± 2 bpm
- 2) Accuracy of the changes in the rTV calculated by CPM System compared to reference TV
 - Root Mean Squared (RMS) of residual relative error after linear fitting.
 - Correlation coefficient between reference device's TV and test device's rTV within subjects

*Secondary Outcome Measures**

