Upon arrival to the clinic on the day of the study visit, prior to the application of the reference and test devices, skin inspection of the application site will be conducted. The CPM Device will then be applied to the participant's chest as described in the IFU materials supplied with the device (the study team will also have received training on the proper placement of the device prior to the initiation of the study). This device will be worn for the entirety of the clinic visit (without removal and replacement). The reference device will also be used for each measurement taken during the visit, concurrently. On the CRF, the time that the CPM Device is placed on the chest will be denoted.

A Baseline measurement will then be initiated using the CPM Mobile Application in order to assign a system-generated patient ID to the participant as well as to establish the tilt angle for the following measurements. The first half of the measurement should be in the Fowler, sitting-upright position, and the second position should be in a Supine, lying-flat position. The reference device will also be used during this time to establish a respiration baseline.

The exercises below will then be followed, with the time of the start of each exercise recorded in the CRF. Four different versions of the exercises (Procedures A-D) will be available that differ only in the sequence of the measurements. The study staff will randomly select a procedure version, using the EDC. Only one procedure version per subject is used. The selected version for each subject will be recorded.

Each exercise will last approximately 4 minutes, or the time that it takes to complete one full measurement with the CPM device in measurement mode (initiated by the CPM mobile app). Within each measurement, participants will move through two positions, both upright and supine. Reference respiration data will be taken concurrently with the CPM device measurement. For each measurement, it is ensured that the reference device recordings are stabilized before initiating the CPM measurement sequence.

For items 1-17, capnography waveform and breath-by-breath reference tidal volume from a metabolic cart will be simultaneously recorded for comparison. For item 18, a diagnostic ECG and clinical grade temperature sensor data will be collected simultaneously.

<Procedure A>

Item	Respiration Rate	Tidal Volume	Mode	Duration
1	Natural (baseline)	Natural (baseline)	Doctor Setup, App	4 min

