In addition, based on the prior study, the root mean squared residual relative errors after linear fitting ranges between 25.2 and 30.4%. To demonstrate that the root mean squared residual errors after liner fitting is less than 35% based on the hypothesis testing Chi-squared test with significance level ($\alpha=0.05$) and 95% power ($\beta=5\%$), the minimum sample needed is 136. Given that 8 readings will be collected per each participant, the minimum number of subjects is 17.

However, to better reflect a broader patient population and since we might be under-estimating our error, we plan to enroll 40 subjects (up to 60 subjects, if necessary).

Data Analysis Plan:

Demographics:

A table will be constructed with counts and percentages of the number of subjects who were screen failures, the number of subjects enrolled in the study, the number of subjects withdrawn from the study before study completion, and the number who completed the study. For those subjects who withdrew before completion of the study, counts and percentages of the reasons for withdrawal will be tabulated. The continuous demographic characteristics at screening will be summarized for all subjects enrolled in the study using descriptive statistics (mean, standard deviation, median, minimum, maximum, and number of non-missing observations). The categorical baseline characteristics will be summarized for the study participants using frequency counts and percentages.

Effectiveness and Endpoint Analyses:

Respiration rate and relative tidal volume from the CPM System will be derived from the CPM analytics engine as described previously in the protocol, and the equivalent parameters and study data will be recorded from the reference device output. The reference respiration rate will be derived by trained medical professional annotating the number of breathing cycles in the recorded capnography waveform in the time period corresponding to the CPM readings.

For pairs of respiration rate calculated by the CPM and the reference, Bland-Altman analysis will be conducted to evaluate the accuracy of the respiration rate.

For pairs of relative tidal volume (rTV) calculated by the CPM system and tidal volume measured by the reference device, the correlation coefficient and R^2 value for the tidal calculated. In addition, the root mean squared of the residual errors after linear fitting will be calculated to characterize the relative errors of the relative tidal volume.

Endpoints:

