For each subject, relative tidal volume from the CPM system and the tidal volume from the reference device under the breathing-depth controlled condition (natural ~ 500 mL, shallow ~ 250 mL, deep ~ 750 mL, very deep >1 L) and the breathing-rate controlled condition (e.g., 10, 15, 25, 30 bpm) will be compared for each body posture. A scatter plot of relative tidal volume produced by the CPM system and the tidal volume measured by the reference device will be produced. Each graph will be summarized by two least-squares linear regression fits. One is produced in a linear scale and the other is produced in a log scale to characterize the relative accuracy.

Analysis 2-1: Respiration rate error descriptive statistics

The descriptive statistics includes but not limited to:

- Percentage of the CPM system's rTV estimate not reported due to bad signal quality.
- Mean, median, variance, standard deviation, skewness, kurtosis, root mean squared error, and root median squared error.

Analysis 2-2: Least-squares linear regression analysis in rTV and TV

The accuracy of relative changes of rTV will be summarized by Pearson correlation coefficients across subjects. Then, mean correlations will be determined using Fisher's z-transformation to combine the subject specific coefficients and then back transformed. A 95% confidence interval on mean correlation coefficient will also be derived.

Analysis 2-3: Least-squares linear regression analysis in natural logs of rTV and TV

The accuracy of relative changes of rTV will be summarized by Pearson correlation coefficients across subjects obtained using natural logs of rTV and TV. Then, mean correlations will be determined using Fisher's z-transformation to combine the subject specific coefficients and then back transformed. A 95% confidence interval on mean correlation will also be derived.

After the linear fit, root mean square of the relative residual errors will also be characterized. A 95% confidence interval on the root mean squared relative errors will also be derived using Chi-squared distribution assuming the relative residual errors follows a zero-mean Gaussian distribution.

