If the root mean square of the relative errors from Analysis 2-3 and its confidence interval does not exceed 35% per end-point in the protocol (CEPR0002), it is demonstrated that the CPM system's relative tidal volume is sufficiently accurate in following relative changes in comparison to the reference. Mean correlation coefficients from Analysis 2-2 and 2-3 will also support that the primary objective of this Analysis 2 is achieved.

Analysis 3: ECG and Skin Temperature Capabilities

The primary objective of this analysis is to evaluate the secondary objectives regarding the ECG and skin temperature capabilities of the CPM system. For skin temperature, the descriptive analyses will be performed in comparison the reference measurement For ECG capabilities, if the data is available, the quality of the CPM ECG can be evaluated.

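### The tidal-volume success rule uses an in-sample RMS of residuals with no stated deduction for the fitted lines; read literally with lines by subject, it runs 6.5% to 13.4% low and passes a true 35% error far too often

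*SAP*

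**What the plan says.** SAP Analysis 2 sets up the comparison by subject: "For each subject, relative tidal volume from the CPM system and the tidal volume from the reference device under the breathing-depth controlled condition", and likewise for the rate-controlled readings, for each posture. It continues: "Each graph will be summarized by two least-squares linear regression fits", one on the linear scale and one on the log scale. Analysis 2-3 then says of the log-scale fit: "After the linear fit, root mean square of the relative residual errors will also be characterized". The 95% interval comes from a chi-squared distribution, with the residuals taken as Gaussian and centred on zero.

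The decision rule that closes Analysis 2 begins "If the root mean square of the relative errors from Analysis 2-3 and its confidence interval does not exceed 35" (per cent). The protocol's primary outcome measure is worded the same way: "Root Mean Squared (RMS) of residual relative error after linear fitting".

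On the amount of data, the protocol's Sample Size Justification says "Given that 8 readings will be collected per each participant, the minimum number of subjects is 17", and its Study Procedures say "Within each measurement, participants will move through two positions, both upright and supine". A subject therefore gives at most 8 readings per posture, or 16 in all. Analysis 2-1 expects some losses, since it lists "Percentage of the CPM system's rTV estimate not reported due to bad signal quality".

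Neither document states the divisor of the RMS, the degrees of freedom of the interval, whether the two postures share a line, or a minimum number of readings per line.

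**The concern.** A fitted line is drawn towards the points it is fitted to. Residuals taken from those same points are smaller than the error of a reading about the true line, and the shortfall is large when each line rests on few points. A literal root mean square divides by the number of residuals and makes no allowance for the slope and intercept estimated for each line. A chi-squared interval that treats the residuals as centred on zero, with nothing deducted, carries the same shortfall into its upper limit.

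This is the only numerical success rule given for the rTV primary endpoint. If the statistic is understated, a device whose error sits exactly at the limit can pass most of the time. Adding subjects makes this worse, because the interval narrows around a figure that is too low. Losing readings also favours a pass, because shorter lines fit more closely.

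**Working it through.** **Inputs from the documents.** 8 readings per subject and 40 subjects, up to 60 (protocol, Sample Size Justification); 2 postures (protocol, Study Procedures); 35% limit on the RMS and its 95% interval (SAP, end of Analysis 2); prior RMS of 25.2% to 30.4% (protocol, Sample Size Justification).

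**Assumptions.** Independent Gaussian log residuals with standard deviation σ; two-sided 95% interval; two parameters per line; divisor and degrees of freedom both equal to N, the total number of residuals.

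**The plan's own figure.** The protocol gives 136 readings, and 136/8 = 17 subjects. A chi-squared test of 35% against 30.4% with 95% power needs 275 readings at one-sided α = 0.05, or 332 two-sided, so 136 does not reproduce. It comes close only if each reading is counted as two posture values (275/2 ≈ 138), which the text does not say. This is a separate matter, and nothing below depends on it.

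**Bias.** For a line through n points, E[RSS] = (n − 2)σ², so the RMS estimates about σ√((n − 2)/n).
- n = 8: √(6/8) = 0.866, 13.4% low; a true 35% reads as 30.3%.
- n = 16: √(14/16) = 0.935, 6.5% low; a true 35% reads as 32.7%.

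**Effect on the rule.** With L lines, RSS/σ² follows chi-squared on N − 2L degrees of freedom. The upper limit is RMS × √(N/χ²(0.025, N)), so

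P(pass | σ) = P(χ²(N − 2L) ≤ χ²(0.025, N) × (35/σ)²).

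The pass probability falls to 2.5% at σ = 35 × √(χ²(0.025, N)/χ²(0.025, N − 2L)). For 8 points and both postures this is 35 × √(571.79/421.19) = 40.8%.

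| Fit, 40 subjects | N | L | N − 2L | Expected upper limit at true 35% | Pass at true 35% | True error at which pass = 2.5% |
|---|---|---|---|---|---|---|
| 8 per line, one posture | 320 | 40 | 240 | 32.9% | 92.6% | 41.0% |
| 8 per line, both postures | 640 | 80 | 480 | 32.1% | 99.8% | 40.8% |
| 16 per line | 640 | 40 | 560 | 34.6% | 64.4% | 37.6% |

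With 60 subjects the pass probabilities are 98.6%, above 99.9% and 81%. A simulation of 1,000 trials with 40 subjects gave 99.7% (8 per line, both postures) and 64% (16 per line). One line pooled over all subjects gives a bias of 0.2% to 0.3% and a pass probability of about 3%.

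**Lost readings.** Starting from 8 per line, the RMS is 15.5% low with 7 left, 18.4% with 6, 22.5% with 5 and 29.3% with 4. With 2 left the residuals are exactly zero, the correlation is ±1 and Fisher's z is infinite. The documents give no loss rate. Under assumed random losses of 10%, 25% and 40%, the simulated pass probability at a true 35% was 68%, 79% and 87% with 16-point lines, and 99.9% or more with 8-point lines.

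**Corrected statistic.** With s = √(ΣRSS/Σ(nᵢ − 2)) and the interval on Σ(nᵢ − 2) degrees of freedom, a true 35% passes 2.5% of the time (1.9% to 4.1% in simulation). Power at a true 30.4% with 40 subjects is 86% (240 degrees of freedom), 99.2% (480) or 99.7% (560). If only the interval's degrees of freedom are corrected and the RMS still divides by N, a true 35% still passes 87%, 99% and 59% of the time in the table's order.

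**The case against.** The strongest reply is that the documents are silent rather than wrong. An analyst who used n − 2 per line in both the estimate and the interval would have no bias. That stands: the error follows from the literal wording and is not a stated computation. But a literal RMS with residuals centred on zero points to N, and leaving the choice open lets the false-pass rate range from 2.5% to 99.8%.

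The fit unit is also unstated. The protocol attaches its within-subject wording to the correlation, not to the RMS, so a pooled line is not excluded. Still, the SAP's by-subject sentence and its reference to each graph make by-subject lines the more natural reading.

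A reader might infer that the 35% limit accepts true errors of 35/0.935 = 37.4% or 35/0.866 = 40.4%. The documents do not support that, because the interval must clear 35% as well as the estimate. With N = 640, the pass probability is only about 3.4% at 37.4% (16 per line) and 4.5% at 40.4% (8 per line).

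On lost readings, the protocol's Study Procedures require a measurement with an unresolved contact or tilt error to be repeated. This limits losses but does not remove them, since the SAP still expects unreported rTV values. Lines with only 2 readings are an edge case.

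Finally, the 2.5% benchmark is inferred from a two-sided 95% interval. The protocol gives α = 0.05 for this test without saying whether it is one- or two-sided.

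**Conclusion.** The point holds on the natural reading of the SAP. The statistic is 13.4% low with 8 readings per line and 6.5% low with 16. At 40 subjects a true 35% error passes about 99.8% (8 per line, both postures), 93% (8 per line, one posture) or 64% (16 per line) of the time, against 2.5% for a correct interval. The rule regains a 2.5% pass rate only near a true 41% or 37.6%.

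This rests on by-subject lines, N as both divisor and degrees of freedom, and independent Gaussian log residuals. It would not hold for one pooled line, or if n − 2 per line were used throughout. Losses add to the bias by an amount the documents do not allow one to fix.

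The planning range may share the problem. If the prior 25.2% to 30.4% was computed the same way (an assumption), dividing by 0.866 gives 29.1% to 35.1%, and by 0.935 gives 26.9% to 32.5%. The upper end would then be close to the limit, or at it.

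**What to change.** In Analysis 2-3 and in the decision rule that closes Analysis 2:

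- State the fit unit: one line per subject and posture, or one per subject.
- Replace the RMS by s = √(ΣRSS/Σ(nᵢ − 2)) over all fitted lines.
- Compute the chi-squared interval from s with Σ(nᵢ − 2) degrees of freedom. Estimate and interval must change together.
- Tabulate the readings and lines lost. Short lines do not bias s, so it needs no minimum. For the Fisher-z averages, use only lines with at least 4 readings if the weights are based on 1/(n − 3).
- Align the endpoint wording in the protocol's Primary Outcome Measures and Endpoints sections.

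The cost is wording in both documents and a few lines of code, with no new data. The reported error becomes larger in relative terms by about 7% (1/0.935) with 16 readings per line, or 15% (1/0.866) with 8. The prior 25.2% to 30.4% range is comparable only if it is recomputed the same way.

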Respiration Rate Accuracy

- 85% respiration rate error $\leq \pm 2$ BPM between reference and test device at 6-40 BPM

Relative Tidal Volume Relative Accuracy

- Root Mean Squared (RMS) of residual error after linear fitting $\leq 35\%$

Respiration Rate Endpoint Justification

The Respiration Rate is derived by the CP Analytics Engine from impedance measurements taken by the CPM device for a one (1) minute period. The CP Analytics Engine performs a quality control (QC) check for at least 30 seconds of consecutive impedance measurement samples. This QC-validated measurement data of at least 30 seconds results in a maximum computational accuracy of 2 BPM for the respiration rate. Consequently, an accuracy of 2 BPM is deemed sufficient for the CPM Device's intended use.

Relative Tidal Volume Endpoint Justification

Relative Tidal Volume as measured by an implanted device have shown to have day-to-day variability ranges between 10% and 14% in terms of coefficient of variation (Boehmer et al., *Journal of Cardiac Failure*, vol. 18, no. 8S, Aug, 2012). In addition, breath-to-breath tidal volume variability ranges from 18% to 43% depending on the underlying pulmonary disease conditions (Kuratomi et al. *Japanese Journal of Medicine*, vol. 24, no. 2, May, 1985), which further supports that day-to-day variability can be as high as 14%. Given this physiological day-to-day variability, it is considered that as high as 35% (about 2.58 times, $Z_{99.5\%}$, of 14%) of change can be

considered physiologic unless other clinical information strongly indicates otherwise. To correctly indicate the change greater than 35%, the relative error less than 35% is deemed sufficient to trend and indicate clinically significant change of rTV.

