Using the data that are classified by the CPM system as good quality, the percentage of the respiration rate whose error is within ± 2 brpm is derived. The confidence interval for the proportion of the errors within ± 2 brpm will also be characterized assuming that the number of data points whose errors are within ± 2 brpm follows binomial distribution.

Analysis 1-3: Respiration rate error limits of agreement

The limits of agreement will be derived using a conventional Bland-Altman analysis as well as non-parametric approach in case the distribution of the error has a long-tail, significant deviation of Normality assumption of the conventional Bland-Altman analysis.

The 85% limits of agreement (bias \pm 1.44 standard deviation) will be tabulated. The 95% confidence interval for the limits of agreement will also be derived. In case the kurtosis, calculated in the Analysis 1-1, is high indicating that the distribution of errors has a long tail, non-parametric limits of agreement will also be presented to correctly characterize the range which 85% of the errors are expected to be bounded by. The non-parametric 85% limits of agreement will also be derived based on 7.5% and 92.5% percentile of the errors. The 95% confidence interval for non-parametric limits of agreement will be derived using a bootstrap resampling method.

Analysis 1-4: Other respiration rate accuracy analyses

A 95% confidence interval (CI) for mean error (i.e., bias) will be tabulated. While the primary objective is to show that the CPM estimate is accurate within ± 2 brpm, the CI for mean error will additionally show if there is any systemic bias in the CPM estimate. The standard deviation of the paired differences will also be tabulated.

If the lower bound of the 95% confidence interval for the percentage of the errors within ± 2 bpm from Analysis 1-2 exceeds 85%, it is demonstrated with statistical significance that the CPM system's respiration rate accuracy is sufficient in comparison to the reference to support its intended use. Also, the other analyses should provide different lenses to characterize the respiration rate accuracy.

Analysis 2: Accuracy of relative changes of relative tidal volume

The primary objective of this analysis is to demonstrate the CPM system's relative tidal volume (rTV) is accurately tracking true changes in tidal volume (TV).

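### The chi-squared interval in the rTV pass rule needs equal residual variance across subjects; if subjects differ it is too narrow, and false success exceeds the nominal 2.5% by an amount the documents do not determine

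*SAP*

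**What the plan says.** SAP Analysis 2-3 regresses log rTV on log TV and summarises the residuals by their root mean square. Of the 95% interval for this summary, the SAP states that it "will also be derived using Chi-squared distribution assuming the relative residual errors follows a zero-mean Gaussian distribution". The decision rule at the end of Analysis 2 begins "If the root mean square of the relative errors from Analysis 2-3 and its confidence interval does not exceed 35" per cent, and meeting it counts as demonstrating sufficient accuracy. The upper 95% limit is therefore the effective pass/fail statistic.

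The protocol's Endpoints section, under "Relative Tidal Volume Relative Accuracy", sets the same 35% limit without mentioning an interval. Its Sample Size Justification frames the claim as a chi-squared test.

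The SAP does not write that the residual SD is common to all subjects; the chi-squared method implies it. Nor does it state the degrees of freedom, how residuals are pooled over subjects and postures, or any alternative if the assumption fails. Analysis 2-1 lists skewness and kurtosis, but nothing follows from them. The only resampling method in the SAP is for respiration rate, in Analysis 1-3: "The 95% confidence interval for non-parametric limits of agreement will be derived using a bootstrap resampling method".

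**The concern.** A chi-squared interval for a variance does not become robust as the sample grows. If some people are tracked well and others poorly, the pooled mean square depends on which people were enrolled, and the interval ignores that source of variation. Such differences are plausible here, because the protocol seeks a range of body types and BMIs.

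At stake is the error rate of a primary endpoint. A device whose true RMS sits at the 35% limit should pass 2.5% of the time; with too narrow an interval it passes more often, and the reported precision of the RMS is overstated. The population of subjects is the relevant target: the study supports a 510(k) submission, and the protocol gives wider representation as one reason for enrolling 40.

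**Working it through.** **The plan's own figure.** The protocol states that "the root mean squared residual relative errors after linear fitting ranges between 25.2 and 30.4" per cent and, for a chi-squared test at alpha 0.05 with 95% power, that "the minimum sample needed is 136" (17 subjects x 8 readings). Taking 30.4% against 35%, the smallest n with P(chi2_df <= chi2_(alpha,df) x 0.35²/0.304²) >= 0.95 is 275 (one-sided 0.05) or 332 (one-sided 0.025). I could not reproduce 136. This does not affect the present point: 40 subjects give 320 readings, or 640 if postures count separately, with 94% or 99.9% power under the chi-squared model at the 0.025 bound.

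**Inputs from the documents.** 40 subjects (up to 60); 8 rTV readings each; 2 postures; limit 35%; two-sided 95% interval.

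**Inputs assumed.** One fitted line per subject and posture, so 2 x (8 - 2) = 12 residual df per subject and 40 x 12 = 480 in all. Residuals are Gaussian within a subject, and subject variances are gamma-distributed with the CVs shown. CV here refers to the variance; 0.5-1.0 corresponds to a CV of the SD of about 0.25-0.52.

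**SAP rule.** Pass if sqrt(SSE / chi2_(0.025,480)) <= 0.35. With chi2_(0.025,480) = 421.2, the observed RMS must be at most 35% x sqrt(421.2/480) = 32.8%.

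**Why it is too narrow.** With d residual df per subject, a subject's mean square has relative variance 2/d + CV²(1 + 2/d). The chi-squared method allows only for 2/d. The ratio is 1 + CV²(1 + d/2), which is 1 + 7CV² for d = 12. The number of subjects does not appear in it, so 60 subjects do not cure the problem. Approximate false success is Phi(-1.96 / sqrt(1 + 7CV²)).

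**Results at a true RMS of 35%:**

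| Variance CV (assumed) | 1 + 7CV² | Normal approximation | Simulated, SAP rule | Simulated, subject-level interval |
|---|---|---|---|---|
| 0 | 1.00 | 2.5% | 2.5% | 3.0% |
| 0.3 | 1.63 | 6.2% | 6% | 3.6% |
| 0.5 | 2.75 | 11.9% | 12% | 4.1% |
| 0.75 | 4.94 | 18.9% | 20% | 4.4% |
| 1.0 | 8.00 | 24.4% | 26% | 5.0% |

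Two-sided coverage of the chi-squared interval at CV 0.5 / 0.75 / 1.0 is about 76% / 62% / 51%. If 10% of subjects have twice the SD of the rest, the SAP rule passes falsely about 18% of the time with either 40 or 60 subjects, and the subject-level interval about 8% with 40. Heavy tails alone (t with 6 df, equal variances) give about 8% and 4%.

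**Sensitivity to the assumed shape.** With lognormal subject SDs (CV of the SD 0.1 to 0.5), the SAP rule gives 3.6% to 26.5% with 8 residuals per subject and 4.7% to 33.2% with 16.

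**The case against.** The strongest objection is that the size rests wholly on an assumption. Seeking varied body types does not establish any particular spread, and a variance CV of 1.0 is extreme: the 10th and 90th percentile subjects would differ 4.7-fold in SD. This stands. A reader might infer that the plan's true false-success rate is 12% or more; the documents do not support that, and at CV 0.3 it is about 6%.

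Other stronger readings also fail.

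- **Kurtosis.** One might explain the inflation by excess kurtosis alone, with a width error of sqrt((2 + kurtosis)/2). For gamma variances the excess kurtosis is 3CV², which gives only 4.7% / 7.4% / 10.8% at CV 0.5 / 0.75 / 1.0. Most of the inflation arises because readings in a subject share a variance, so the point overlaps with within-subject clustering.
- **Breath depth.** Every subject performs the same set of depths, so this difference is fixed by design. Doubling the SD at 250 mL gives 3.5%, and at 750 and 1000 mL 4.8%.
- **The respiration-rate bootstrap.** One might say the SAP already protects its other primary pass rule. The Analysis 1-3 bootstrap serves the limits of agreement, whereas the respiration-rate pass rule is a binomial interval. Nor is that bootstrap said to resample subjects.

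If inference is limited to the enrolled subjects, false success is only about 3.9% / 5.6% / 7.8% at CV 0.5 / 0.75 / 1.0. That is a coherent position, but narrower than the study's stated purpose.

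**Conclusion.** The concern holds in conditional form. The SAP ties a primary pass rule to an interval that is valid only for independent, Gaussian residuals of equal variance across subjects, and nothing in the plan compensates if that fails. With equal variances the rule works as designed. If subjects differ, false success rises to about 6% at a variance CV of 0.3 and about 26% at 1.0, under the layout and df assumed above. The direction is certain once subjects differ; the size is unknown until subject-level residuals are seen. The change is worth making before analysis, but the documents do not show that the endpoint's error rate is in fact inflated.

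**What to change.** In Analysis 2-3, base the 35% rule on an interval with the subject as the unit:

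1. For each subject, compute the residual mean square (residual sum of squares over that subject's residual df).
2. Take the arithmetic mean m of these across subjects, and its standard error se.
3. Form m x exp(± t x se/m), with t on (number of subjects - 1) df, and take square roots. Apply the 35% rule to the upper limit.

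Bootstrapping whole subjects on the pooled mean square is an alternative; a percentile bootstrap gives about 4-7% false success in the CV cases.

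The wording must exclude averaging the logs of the subject mean squares. That targets the geometric mean and passes falsely about 22% of the time with equal variances, and 49% / 73% / 90% at CV 0.5 / 0.75 / 1.0.

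Keep the chi-squared interval as descriptive, tabulate the subject-level RMS, and state the pooling and residual df in the same edit.

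**Cost.** SAP wording and a few lines of code; no new data. The interval widens if subjects differ. At a true RMS of 30.4%, power at CV 0.3 / 0.5 / 0.75 is about 91% / 75% / 55%, against 97% / 94% / 87% for the chi-squared rule, part of whose power is false precision. At 25.2% it stays at 94% or more up to CV 1.0. With equal variances power is essentially unchanged. The sponsor should weigh this against the protocol's 95% power target, and against the option of enrolling up to 60.
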